6.4.6 Treatment Period

Data collected on the Date of the First 3005 LCIG Infusion (Day 1) will be assigned to the Baseline Period. However, adverse events and concomitant medications starting on Day 1 will be assigned to the Treatment Period (worst case scenario).

A Gap Period (number of days) is defined to include data collected after the end of the relevant Treatment Period in the analysis. For this study, the Gap Period will be 30 days for adverse events and 1 day for all other assessments.

For efficacy assessments the Treatment Period is defined as the Period from the Date of the First 3005 LCIG Infusion up to and including the Date of the Last 3005 LCIG Infusion + Gap Period (1 day). For safety assessments the Treatment Period is defined as the Period from the Date of the First 3005 LCIG Infusion up to and including the Date of the Last 3005 PEG-J Exposure + Gap Period (30 days for adverse events and 1 day for all other assessments).

The Endpoint value for a variable is defined as the last non-missing value assigned to the Treatment Period for the subject.

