6.4 Day Numbers, Study Periods and Visit Windows: Related Definitions

6.4.1 General Definitions

Assessment days will be related to the date of the first infusion of 3005 study drug (First 3005 LCIG Infusion). Baseline is defined in Section [6.4.5](#) (Baseline Period). The Cutoff Date for the 2015 interim analysis will be 30 September 2015. Assessments and/or measurements performed after the Cutoff Date, adverse events or device complications with start dates after the Cutoff Date, and concomitant medications with start dates after

the Cutoff Date will not be included in the 2015 interim analysis. No cutoff date will be applied to the analysis for the final CSR.

The following reference dates will be defined for all subjects in the All Subjects Consented subject sample defined in Section 8.1.1.

- **Date of the First 3005 LCIG Infusion (Day 1, RFSTDTN):**

The actual dates of study drug administration are not recorded in the 3005 database. The dates when 3005 study drug is dispensed are recorded in the DA raw data panel. For analysis, the date of the first 3005 LCIG infusion will be defined as the first date that 3005 study drug was dispensed to the subject. The visit date recorded in the DM raw data panel will be used if the date the first study drug was dispensed is not available.

The date of the first 3005 LCIG infusion will be defined as Day 1 and is the key variable RFSTDTN and is used in the calculation of relative days.

- **Date of the Last 3005 LCIG Infusion (RFENDTN):**

For subjects who have prematurely discontinued or completed the study, the date of the last 3005 LCIG infusion will be the earliest of 1) the date of last study drug administration collected on the DS raw data panel, 2) the date of discontinuation or study completion collected on the DS raw data panel and 3) the Cutoff Date (interim analysis only).

For the 2015 interim analysis, the date of the last 3005 LCIG infusion for all ongoing subjects will be the Cutoff Date.

- **Duration of 3005 LCIG Infusion (LDA):**

The Duration of 3005 LCIG Infusion or exposure to treatment is equal to the day number of the Last 3005 LCIG Infusion (LDA) and is derived as follows from the previous two dates:

$$\text{LDA (days)} = (\text{Date of the Last 3005 LCIG Infusion [RFENDTN]} - \text{Date of the First 3005 LCIG Infusion [RFSTDTN]}) + 1$$

LDA then indicates the relative day of the last 3005 LCIG infusion for each subject.

- **Date of Last 3005 PEG-J Exposure (RFENDT2N):**

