LCIG is administered as part of a therapeutic system that includes devices and implantation procedures. Subjects who discontinue LCIG therapy are to have their PEG-J removed.

For subjects who have prematurely discontinued or completed the study, and have reported a final PEG-J removal on the DI raw data panel that is after their last day of study drug administration and before the Cutoff Date (interim analysis only), their date of last 3005 PEG-J exposure will be the date of PEG-J removal. For all other subjects who have prematurely discontinued or completed the study, their date of last 3005 PEG-J exposure will be the earlier of 1) the date of discontinuation or study completion collected on the DS raw data panel, and 2) the Cutoff Date (interim analysis only).

For the 2015 interim analysis, the date of the last 3005 PEG-J exposure for all ongoing subjects will be the Cutoff Date.

The date of the last 3005 PEG-J exposure is the key variable RFENDT2N.

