8.5.5 Other Safety Analyses

Other safety data, not previously discussed, include:

- Complications with infusion device
- PEG tube and J tube replacements and average duration
- Sleep attacks
- Minnesota Impulsive Disorders Interview (MIDI)
- Columbia Suicide Severity Rating Scale (C-SSDRS)
- Melanoma check
- Neurological examination

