8.5.5.1 Complications with Infusion Device

For each complication related to the infusion device (i.e., tubing kinks, tubing displaced, tubing connector problems, and pump technical difficulties) the following data will be collected in addition to a description of the complication.

- Incident start and stop date
- Type of complication
 - Pump complication

- Intestinal tube complication
- PEG-J complication
- Stoma complication
- Other complication
- Action taken
 - No action taken
 - Reposition of tube with surgery
 - Reposition of tube without surgery
 - Pump replaced
 - Medication treatment interrupted
 - Medication treatment stopped
 - Other
- Did this complication result in an AE? ("Yes" or "No")
- For complications that resulted in an AE, the AE number(s)

Each device complication will be assigned to a Preferred Term (PT), according to the MedDRA thesaurus, Version 14.0.

The percentage of subjects with a device complication will be determined as the number of subjects with at least one device complication relative to the number of subjects at risk. A subject will be considered at risk if the subject is in the Safety subject sample. Summaries of device complications by action taken will exclude complications where the response for action taken is "No action taken."

The incidence of device complications during each 3005 Treatment Year will be summarized using the study day intervals described in Section 6.4.9. Device complication start days and Treatment Period end days will be calculated relative to the start of 3005 LCIG infusion (RFSTDTN) as follows:

$$\text{Device Complication Start Day} = (\text{Device Complication Start Date} - \text{Date of First 3005 LCIG Infusion}) + 1$$

$$\text{Treatment Period End Day} = ([\text{Date of Last 3005 PEG-J Exposure} + 30 \text{ Days}] - \text{First Date of 3005 LCIG Infusion}) + 1$$

The count (and numerator for percentage calculations) will be the number of subjects who had their first occurrence of the PT start within the study day range for the 3005 Treatment Year. Each subject will be counted at most once within each SOC and PT.

The denominator for percentage calculations will include all subjects whose Treatment Period End Day is within or greater than the study day range for the 3005 Treatment Year.

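### The by-year denominators for device complications and tube replacements add 30 days, where the SAP's own gap for non-AE data is 1 day; at the interim the added days fall after the data cutoff

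*SAP*

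**What the plan says.** SAP 6.4.6 fixes the window after treatment: "the Gap Period will be 30 days for adverse events and 1 day for all other assessments". The same two values are repeated in the definition of the safety Treatment Period and in 6.4.7. Section 8.5.5 lists device complications and tube replacements among the other safety data, apart from adverse events.

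Sections 8.5.5.1 and 8.5.5.2 compute a Treatment Period End Day as the date of last PEG-J exposure plus 30 days, counted from the first infusion in this study. This is the formula of the adverse-event section, 8.5.1. The by-year denominator then takes in "all subjects whose Treatment Period End Day is within or greater than the study day range for the 3005 Treatment Year". It feeds tables DCT003, DCT006 and DIT002. Section 10.1, which records changes to planned analyses, does not mention it.

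For the 2015 interim, 6.4.1 says that "the date of the last 3005 PEG-J exposure for all ongoing subjects will be the Cutoff Date". The same section excludes "adverse events or device complications with start dates after the Cutoff Date".

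**The concern.** Two rules in one SAP give different end days for the same data, and the longer one adds time in which some subjects can contribute no event. They enlarge the denominator and leave the numerator unchanged, so the percentage falls. The effect is concentrated in the later years, where few subjects remain and where long-term device safety, a secondary objective, is read.

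The SAP handles the matter differently elsewhere. The yearly denominator for concomitant medication (8.2.4) uses the last infusion day with no gap. EXT001 (9.8) counts a subject in a year only if exposure reached into it by at least one day. The report could therefore show more subjects at risk of a device complication in a year than subjects with PEG-J exposure in that year.

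**Working it through.** The plan states no rate or denominator on this point, so there is no figure to reproduce.

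**Who is added.** Let L be the day number of last PEG-J exposure: last date − first infusion date + 1. The SAP formula reduces to End Day = L + 30. With the 6.4.6 gap it would be L + 1. A subject enters the year starting on day B if the End Day is at least B. With the boundaries of SAP Table 3:

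| Year | Starts on day | 30 days: enters if L ≥ | 1 day: enters if L ≥ |
|---|---|---|---|
| Year 2 | 366 | 336 | 365 |
| Year 3 | 731 | 701 | 730 |
| Year 4 | 1096 | 1066 | 1095 |
| Year 5 | 1461 | 1431 | 1460 |
| Beyond Year 5 | 1826 | 1796 | 1825 |

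Each boundary has a 29-day band (29/365 = 7.9% of a year); for the last category it is days 1796–1824. Year 1 does not change.

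**Whether they can have an event.** After an actual PEG-J removal there is no tube to replace. At the interim, an ongoing subject's L is set at the Cutoff Date, so all 30 added days lie after it, where device complications and adverse events are excluded. Tube placements are not named in that exclusion; I read them as covered by the rule on assessments. The by-year adverse-event denominators (8.5.1; AET011, AET014) run past the cutoff in the same way.

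**Size, closed form.** Assume a share q of those at risk in a year end exposure in that year, spread evenly. The next year's denominator, per subject at risk, is (1 − q) + q × 1/365 with 1 day and (1 − q) + q × 30/365 with 30 days. For q = 50% this is 0.5014 against 0.5411, a ratio of 1.079. If the percentage with the 1-day gap is 20%:

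| q (assumed) | Denominator inflation | 20% reads as |
|---|---|---|
| 10% | 0.9% | 19.8% |
| 20% | 2.0% | 19.6% |
| 50% | 7.9% | 18.5% |
| 80% | 31% | 15.2% |

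**Size, simulation.** The only documented input is the planned 275 subjects. Dropout, enrolment spread, longest follow-up at the interim and maximum further follow-up to the final analysis are assumptions. Entries are mean denominators with 1 day → 30 days, and the inflation from unrounded values.

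| Dropout/yr; enrolment; longest follow-up; further (years) | Year 2, interim | Year 5, interim / final | Beyond Year 5, interim | Beyond Year 5, final |
|---|---|---|---|---|
| 10%; 3; 6; 1 | 0.8% | 4.9% / 3.9% | 54.3 → 59.1 (8.7%) | 82.0 → 87.1 (6.2%) |
| 10%; 3; 6; 2 | 0.9% | 4.8% / 2.2% | 54.4 → 59.3 (8.8%) | 108.6 → 113.8 (4.8%) |
| 15%; 4; 6; 1 | 1.3% | 5.3% / 4.5% | 30.9 → 33.8 (9.3%) | 46.2 → 49.3 (6.6%) |
| 10%; 2; 5.5; 1 | 0.8% | 6.3% / 2.8% | 41.3 → 48.2 (16.7%) | 81.9 → 89.1 (8.8%) |
| 10%; 4; 5; 1 | 0.9% | 8.9% / 6.0% | 0.3 → 3.6 (ratio not meaningful) | 20.6 → 24.0 (16.7%) |

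The largest stable inflation, 16.7%, lowers a percentage by 1 − 1/1.167 = 14% relative; 4.8% lowers it by 1 − 1/1.048 = 4.6%.

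**The case against.** The strongest reply is that the 1-day gap is written for assessments. SAP 6.4.1 names assessments separately from adverse events and device complications, and 6.4.9 calls device complications and tube replacements events. The 30 days could then be a deliberate rule for event data. It would also keep device complications that led to an adverse event on the same denominator as the procedure- and device-related adverse-event tables. This is a possible intention, but the SAP does not state it. The safety Treatment Period in 6.4.6 and 6.4.7 offers only two gaps and gives the longer one to adverse events alone.

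A reader might infer that no device complication at all can follow the end of PEG-J exposure. The documents do not support that. Stoma complications are a recorded type (SAP 8.5.5.1), and the stoma is inspected at the follow-up visit (Protocol Table 2). The end date is not always a removal either: subjects without a qualifying removal record get their discontinuation or completion date (SAP 6.4.1), and those who transfer to commercial product keep the tube (Protocol 11.0). The numerator in 8.5.5.1 also has no explicit end-of-period limit, so a complication starting 2 to 30 days after the end could be counted in the final analysis. Dilution of the final device-complication percentages is therefore less certain than dilution of the tube-replacement percentages after removal, or of the interim percentages.

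The shift is also modest against sampling error. In the first scenario, 20% on 54.3 subjects would read 20 × 54.3/59.1 = 18.4%, while the 95% half-width at n = 54 is 1.96 × √(0.2 × 0.8/54) = 10.7 percentage points. These are descriptive tables with no formal test.

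**Conclusion.** The point holds as a minor inconsistency with a known direction where no event is possible. Followed exactly, the SAP puts subjects into later-year denominators who cannot contribute a tube replacement after removal or, if ongoing at the interim, any countable device event. The by-year adverse-event denominators share only the interim part, because 30 days is their proper gap otherwise.

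The reach is narrow: DCT003, DCT006 and DIT002, plus AET011 and AET014 at the interim, all from Year 2 on. A reader might infer that the headline device-complication rates are too low. They are not affected, because they use the whole Safety sample.

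No single figure for the bias can be drawn from the documents. The range of about 1% in years with attrition only, and roughly 5–17% beyond Year 5, is denominator inflation under assumed accrual and dropout, and is illustrative. Wherever the ratio could be read, inflation beyond Year 5 was larger at the interim than at the final analysis. In the fifth scenario that category was almost empty at the interim.

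**What to change.** 1. For any interim output, cap every Treatment Period End Day at the Cutoff Date, including those for adverse events in 8.5.1. A 1-day gap alone would still run one day past the data.
2. In 8.5.5.2, define the end day as last PEG-J exposure + 1 day.
3. In 8.5.5.1, use + 1 day for numerator and denominator alike. If 30 days is kept so that complications linked to adverse events match the adverse-event tables, state that reason and limit the numerator to the same window.

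The cost is SAP wording and a few derivation lines, with no new data. With a 1-day gap, the by-year device denominators will differ slightly from those of the adverse-event tables; a footnote can say so.

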6.4.7 Post-Treatment Period

For efficacy assessments, the Post-Treatment Period is defined as the period after the Date of the Last 3005 LCIG Infusion + Gap Period (1 day). For safety assessments, the Post-Treatment Period is defined as the period after the Date of the Last 3005 PEG-J Exposure + Gap Period (30 days for adverse events and 1 day for all other assessments).

6.4.8 Visit Windowing Conventions

Assessments will be assigned to the Baseline Period if the date is on or before the Date of the First 3005 LCIG Infusion as defined in Section 6.4.1 and to the Post-Treatment Period if the date is after the end of the relevant Treatment Period as defined in Section 6.4.6.

Assignment of assessments to visits during the Treatment Period will use visit windows based on the day of the assessment relative to the Date of the First 3005 LCIG Infusion as described in Table 2 below.

Table 2. Visit Windowing Conventions

Visit Label	Target Visit Day	Study Day Range
Baseline	≤ 1	
Month 6	180	2 to 270
Month 12	360	271 to 450
Month 18	540	451 to 630
Month 24	720	631 to 810
Month 30	900	811 to 990
Month 36	1080	991 to 1170
Month 42	1260	1171 to 1350
Month 48	1440	1351 to 1530
Month 54	1620	1531 to 1710
Month 60	1800	1711 to 1890
Month 66	1980	1891 to 2070
Month 72	2160	2071 to 2250
Month 78	2340	2251 to 2430
Month 84	2520	> 2430

If a subject has two or more assessments in the same visit window, the assessment closest to the target visit day will be used. If two assessments are equidistant from the target visit day, the later assessment will be used.

Each reported post-baseline lab and vital sign measurement shall be evaluated to determine if it meets potentially clinically significant criteria. For all other analyses of

labs and vital signs, if two measurements are on the same date, the average will be calculated and treated as the value for that date.

6.4.9 3005 Treatment Year

The following events will be summarized by 3005 Treatment Year using the study day intervals described in [Table 3](#) below: premature study discontinuations, prevalence of concomitant anti-parkinsonian medication use, the incidence and prevalence of adverse events, the incidence of device complications, and the number of PEG tube and J-tube replacements.

Table 3. 3005 Treatment Year

3005 Treatment Year	Study Day Range
Year 1	2 to 365
Year 2	366 to 730
Year 3	731 to 1095
Year 4	1096 to 1460
Year 5	1461 to 1825
> Year 5	> 1825

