The percentage of each of the aforementioned AE types will be determined as the number of subjects with at least one mention of the AE type relative to the number of subjects at risk. A subject will be considered at risk if the subject is in the Safety subject sample.

In addition to the aforementioned AE types, AEs reported by the Investigator as related to device complications will also be summarized. Device complications are captured in the DE raw data panel and associated AEs are captured in the AE raw data panel.

Investigators link the AEs that are related to device complications by entering an AE number in the DE raw data panel.

The incidence and prevalence of TEAEs during each 3005 Treatment Year will be summarized using the study day intervals described in Section 6.4.9. AE start days and Treatment Period end days will be calculated relative to the start of 3005 LCIG infusion (RFSTDTN) as follows:

$$\text{AE Start Day} = (\text{AE Start Date} - \text{Date of First 3005 LCIG Infusion}) + 1$$

$$\text{Treatment Period End Day} = ([\text{Date of Last 3005 PEG-J Exposure} + 30 \text{ Days}] - \text{First Date of 3005 LCIG Infusion}) + 1$$

For summaries of incidence, the count (and numerator for percentage calculations) will be the number of subjects who had their first treatment-emergent occurrence of the PT start

within the study day range for the 3005 Treatment Year. Each subject will be counted at most once within each SOC and PT.

For summaries of prevalence, the count (and numerator for percentage calculations) will be the number of subjects who had a treatment-emergent occurrence of the PT start within the study day range for the 3005 Treatment Year or who had an earlier treatment-emergent occurrence of the PT that had not ended prior to the start of the study day range for the 3005 Treatment Year.

The denominator for both incidence and prevalence percentage calculations will include all subjects whose Treatment Period End Day is within or greater than the study day range for the 3005 Treatment Year.

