8.5.5.2 PEG Tube and J Tube Replacements and Average Duration

The date of each PEG tube and J tube placement and removal is recorded on the Device Information eCRF. The number of PEG tube replacements and the number of J tube replacements overall and by 3005 Treatment Year will be summarized.

The number of PEG tube and J tube replacements during each 3005 Treatment Year will be summarized using the study day intervals described in Section 6.4.9. Tube replacement days and Treatment Period end days will be calculated relative to the start of 3005 LCIG infusion (RFSTDTN) as follows:

$$\text{Tube Replacement Day} = (\text{Tube Placement Date} - \text{Date of First 3005 LCIG Infusion}) + 1$$

$$\text{Treatment Period End Day} = ([\text{Date of Last 3005 PEG-J Exposure} + 30 \text{ Days}] - \text{First Date of 3005 LCIG Infusion}) + 1$$

The count (and numerator for percentage calculations) will be the number of subjects who had one or more PEG (or J) tube replacements within the study day range for the 3005 Treatment Year. Each subject will be counted at most once for each 3005 Treatment Year.

The denominator for percentage calculations will include all subjects whose Treatment Period End Day is within or greater than the study day range for the 3005 Treatment Year.

As previously described, Study 3005 is an extension of the previous Studies 3001, 3002, 3003, and 3004. The number of PEG tube and J tube replacements in these previous studies will be retrieved from the relevant study databases and will be summarized.

The average PEG tube and J tube duration (time in place) during Study 3005 will be summarized. For each tube the duration will be calculated as the tube removal date – the tube placement date +1. The average PEG tube and average J tube duration for each subject will then be calculated as the mean of all PEG (J-tube) tubes the subject had exposure to during the study. For tubes already in place at the start of the study (missing placement date), the placement date will be imputed as the date of the first 3005 LCIG infusion (as defined in Section 6.4.1). For tubes remaining in place (missing removal date), the removal date will be imputed as the date of the last 3005 PEG-J exposure (as defined in Section 6.4.1). Due to the imputation of placement and removal dates, the 3005 tube duration will be interpreted as the minimal amount of time the tube was in place.

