CMT002 The number of subjects with at least one anti-parkinsonian concomitant medication used in the Treatment Period will be presented by time interval (Year 1, Year 2, Year 3, Year 4, Year 5, > Year 5) using default summary statistics, where the percentage of subjects is calculated relative to the total number of subjects considered valid for the specific subject sample, that is, Safety Sample during the given time interval. In addition, the number of subjects with at least one concomitant medication use within each ATC third level subgroup and generic name will be presented. The ATC third level subgroups are to be ordered alphabetically/numerically by ATC code and within ATC third level subgroup alphabetically by generic name.

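### The open-ended '> Year 5' interval in SAP Table 3 can run to about 1.9 years, so its percentages cannot be compared directly with those of the one-year intervals before it

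*SAP*

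**What the plan says.** SAP 6.4.9 sets the time base for the by-year tables: "The following events will be summarized by 3005 Treatment Year using the study day intervals described in" Table 3. The list covers premature discontinuations, use of anti-parkinsonian medication, incidence and prevalence of adverse events, device complications, and PEG and J tube replacements. Table 3 has Year 1 (days 2 to 365), Years 2 to 5 (ending on day 1825) and a last interval defined only as later than day 1825. Table CMT002 in SAP 9.6 repeats the pattern: "by time interval (Year 1, Year 2, Year 3, Year 4, Year 5, > Year 5").

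Three other provisions decide how long the last interval is and how it is counted.

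- **Length of follow-up.** Table 2 in SAP 6.4.8 plans visits to Month 84 (target day 2520), and the Month 84 window is itself open (any day after 2430). SAP 6.4.1 adds: "No cutoff date will be applied to the analysis for the final CSR".
- **Numerators.** Adverse event incidence in SAP 8.5.1 counts "the number of subjects who had their first treatment-emergent occurrence of the PT start" in the interval, and SAP 8.5.5.1 uses a first-occurrence rule for device complications too. Prevalence also counts subjects "who had an earlier treatment-emergent occurrence of the PT that had not ended prior to the start of the study day range". SAP 8.5.5.2 counts "the number of subjects who had one or more PEG (or J) tube replacements within the study day range".
- **Denominators.** For adverse events the denominator is to "include all subjects whose Treatment Period End Day is within or greater than the study day range for the 3005 Treatment Year". SAP 8.5.5.1 and 8.5.5.2 apply the same rule. In all three sections the Treatment Period End Day is the last PEG-J exposure plus 30 days.

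SAP 9.8 (EXT001) reports the number of subjects exposed by yearly interval and the total subject-years. No subject-years by interval, and no rate per subject-year, are planned.

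**The concern.** Protocol 13.1 makes long-term safety the primary statistical objective, and the by-year tables are where a reader will look for a trend. A longer interval collects more subjects with an event even if the underlying risk never changes. The denominator does not compensate: a subject with one day in the interval counts the same as a subject with 695 days. The last interval holds the longest-exposed subjects, and its percentage will be printed beside one-year figures on a different time base. A difference between Year 5 and the period after it could be a change in risk, or only a difference in interval length and follow-up. The summary tables would not let the reader tell which.

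**Working it through.** **Reproducing the plan's boundaries.** 5 × 365 = 1825, the end of Year 5. Year 1 has 364 days (2 to 365), and Years 2 to 5 have 365 each. The Month 84 target is 84 × 30 = 2520.

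**Length of the last interval.**
- To the Month 84 target: 2520 − 1825 = 695 days; 695 / 365 = 1.90 years.
- To the start of the Month 84 window: 2431 − 1825 = 606 days, or 1.66 years.
- To day 2520 plus the 30 days in the denominator rule: 2550 − 1825 = 725 days, or 1.99 years.

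The SAP sets no end, so the interval could also be longer.

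**Assumptions.** The documents give no event rates. I assume a constant annual risk *p*, varied from 5% to 40%, and follow-up to day 2520, so that *L* = 695 / 365 = 1.904 years are spent in the last interval.

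**Formulas.**
- Any occurrence (tube replacement): Year 5 = *p*; last interval = 1 − (1 − *p*)^*L*.
- First occurrence, with earlier cases kept in the denominator as the SAP specifies (adverse event and device incidence): Year 5 = (1 − *p*)^4 × *p*; last interval = (1 − *p*)^5 × [1 − (1 − *p*)^*L*].

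For example, at *p* = 10%, any occurrence is 1 − 0.90^1.904 = 18.2%. First occurrence is 0.6561 × 0.10 = 6.6% in Year 5 and 0.5905 × 0.1818 = 10.7% in the last interval.

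| Annual risk | Any: Year 5 | Any: > Year 5 | First: Year 5 | First: > Year 5 |
|---|---|---|---|---|
| 5% | 5.0% | 9.3% | 4.1% | 7.2% |
| 10% | 10.0% | 18.2% | 6.6% | 10.7% |
| 20% | 20.0% | 34.6% | 8.2% | 11.3% |
| 30% | 30.0% | 49.3% | 7.2% | 8.3% |
| 40% | 40.0% | 62.2% | 5.2% | 4.8% |

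At 10%, a one-year Year 6 would show a first-occurrence incidence of 0.5905 × 0.10 = 5.9%. A series that should fall from 6.6% to 5.9% would be printed as a rise to 10.7%.

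**Partial follow-up.** The documents give no distribution of follow-up. Simulations at 20% annual risk, with end days spread evenly over a range, give:

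| End days | Mean days in last interval | Any: Year 5 vs > Year 5 | First: Year 5 vs > Year 5 |
|---|---|---|---|
| 2190 to 2550 | 545 | 20.0% vs 28.2% | 8.2% vs 9.2% |
| 1825 to 2550 | about 363 | 20.0% vs 19.2% | 8.2% vs 6.3% |
| 1000 to 2100 | 138 | 14.5% vs 8.0% | 6.0% vs 2.6% |

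For first occurrence, each subject needs about 1.05, 1.12, 1.29 or 1.57 years in the last interval (annual risk 5%, 10%, 20% or 30%) before it exceeds Year 5.

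**Would splitting alone be enough?** Take end days spread evenly over 2190 to 2550 and 20% annual risk. A separate Year 7 would hold between 0 and 360 days per subject. With *x* = 0.2231 × 360 / 365 = 0.220, its any-occurrence figure would be 1 − (1 − e^−*x*) / *x* = 10%, against 20% in a full year. Splitting removes the excess length but not the effect of partial follow-up.

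**The case against.** The label tells the reader that the last interval is open. The tables are descriptive, no alpha level is tested (Protocol 13.4), and pooling a sparse tail is ordinary practice. EXT001 gives the number exposed by interval and total subject-years, and listing AEL001 gives the relative day of each event. The protocol expected a duration of approximately 4 years, so few subjects may reach this interval. Any interval is affected by partial follow-up, not only the last one.

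Much of this stands, and it limits the point to presentation. It does not remove it. A label does not adjust a percentage, and a total of subject-years cannot be allocated to intervals. The SAP, whatever duration the protocol expected, plans visits to Month 84. If few subjects stay long past day 1825, the same counting rule errs in the other direction.

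Three stronger readings are tempting but unsupported.

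- **That the tables will show a false late rise in risk.** This needs long follow-up within the interval, which the documents do not describe. With end days spread over 1825 to 2550 there is no rise, and first-occurrence incidence falls.
- **That the any-occurrence figures apply to every listed output.** They fit tube replacement. Adverse event and device incidence follow the first-occurrence rule, where the effect is smaller and reverses at 40% annual risk. Adverse event prevalence and medication use carry earlier items forward, so neither formula fits them exactly. For discontinuations, DST003 states no by-year denominator, so the denominator criticism cannot be extended to it.
- **That the last interval cannot be interpreted at all.** It can be read as a description of what happened after day 1825. What it does not support is a direct comparison with earlier years.

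**Conclusion.** The point holds as a minor weakness of presentation. The last interval in Table 3 is on a different time base from the others, up to about 1.9 times as long on the SAP's own schedule, and nothing planned by interval corrects for that. Under constant risk and follow-up to day 2520, the last interval exceeds Year 5 by a factor of 1.86 to 1.73 for any-occurrence measures (9.3 / 5.0 to 34.6 / 20.0) and by 1.77 to 1.38 for first-occurrence incidence, for annual risks of 5% to 20%. These sizes rest on assumed rates and assumed full follow-up. The actual size and direction cannot be worked out from the documents.

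**What to change.** In SAP Table 3 and in CMT002, replace '> Year 5' with:

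- Year 6: days 1826 to 2190
- Year 7: days 2191 to 2555
- > Year 7: all days after 2555

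The residual is needed because the final analysis has no cutoff date; a table ending at day 2555 would leave later events in no interval.

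Print subject-years at risk for every interval, not only the last. For adverse events, device complications and tube replacements, add events or subjects per subject-year. For first-occurrence incidence, stop a subject's time at risk at the first occurrence. This is the part that deals with partial follow-up. Use the same intervals for 3005 exposure in EXT001 so that the numbers exposed match.

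The cost is SAP wording, two more intervals per by-year table and a subject-years line. No new data are needed. The downside is small numbers in the last intervals, which the subject-years will make visible.
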